1.2.2. Subject Populations for Analysis

Three subject populations will be defined:

Intent-To-Treat population (ITT population): Any subject randomized that received a dose of study drug and had post baseline MSSS data. ITT population are analyzed as they are randomized, regardless of which treatment a subject received.

Safety population (Safety population): Any subject randomized that received a dose of study drug. Safety population are analyzed based on the actual treatment received.

Per-Protocol population (PP population): Any subject who was randomized and received the protocol required study drug exposure and required protocol processing. Blinded clinical data will be reviewed prior to data lock to finalize the list of PP population.

The primary analyses will be performed in the intent-to-treat population. Analyses of efficacy endpoints in the PP population will provide supportive evidence. Safety summaries will be based on the Safety population.

1.2.3. Subject Disposition

Study completion and reasons for discontinuation for all randomized subjects in the doubleblind phase will be summarized for each treatment group by simple tabulation. Discontinuations by reason will be tabulated by visit for each treatment group.

1.2.4. Demography and Other Baseline Data

Demographic data will be tabulated by treatment group. Past and current medical history will be summarized by treatment group using the system organ class (SOC) as coded using the Medical Dictionary for Regulatory Activities (MedDRA) coding dictionary.

1.2.5. Study Medication

Exposure and compliance will be tabulated by treatment groups.

1.2.6. Prior/Concomitant Therapy

Prior/concomitant therapy will be summarized.

Any medications or therapy present before the first dose of study medication will be considered as prior medications. Concomitant medications (medications present while on study medication) will be recorded throughout the study and at early discontinuation. These medications will be coded using the WHO-drug dictionary. The number of subjects from the Safety Set using prior or concomitant medications will be categorized by the WHO-drug category and preferred term, and presented for each treatment group. In any given category (e.g., drug category) a subject will be counted only once.

1.3. Efficacy Data Analysis

1.3.1. Primary Outcome and Methodology

The primary endpoint is motion sickness severity assessed by the MSSS questionnaire. The primary analysis method is ANOVA with the treatment group, vehicle, and site, if more than one site, as main effects. The primary efficacy analysis will be based on the ITT population.

The statistical analyses will be detailed in the statistical analysis plan (SAP).

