VP-VLY-686-2401 Confidential

Motion Sifnos: A Randomized, Double-Blind, Placebo-Controlled Study to Investigate the Efficacy of Tradipitant in Subjects Affected by Motion Sickness during Travel

Document Type:	Clinical Study Protocol
Sponsor:	Vanda Pharmaceuticals Inc. [name]
Study Product:	tradipitant (VLY-686)
Protocol Number:	VP-VLY-686-2401
Study Phase:	II
IND Number:	141315
NCT Number:	NCT03772340

Date: 03 18 2019 **Status:** Final

Name of Sponsor/Company:

Vanda Pharmaceuticals Inc.

Name of Investigational Product:

Tradipitant/VLY-686

Name of Active Ingredient:

Tradipitant/VLY-686

Title of Study: Motion Sifnos: A randomized, double-blind, placebo-controlled study to investigate the efficacy of tradipitant in subjects affected by motion sickness during travel

Study Center(s): 1

Studied Period:	Phase of Development:
First subject enrolled: December 2018	Phase II
Estimated study duration: Four months	

Number of Subjects (planned): Approximately 150 affected subjects will be randomized and assigned to tradipitant 170 mg or placebo in a 1:1 ratio. Treatment assignments will be made according to a randomization schedule. Vehicle travel assessment will occur either in a motor vehicle (2A) or a boat (2B).

Diagnosis and Main Criteria for Inclusion: Adult males or females aged 18-75, inclusive, with a history of motion sickness who meet inclusion criteria.

Investigational Product, Dosage and Mode of Administration: Tradipitant 170 mg PO or placebo once approximately 60 minutes before entering the vehicle.

Duration of Treatment: If motor vehicle travel, one drive lasting approximately 120-240 minutes. If boat travel, one trip lasting approximately 90-300 minutes on the moving vessel.

Reference Therapy, Dosage and Mode of Administration: Placebo capsules will be provided in size and appearance identical to those containing tradipitant and will be administered orally.

Primary Objectives:

1. To assess the effects of tradipitant 170 mg on the symptoms of motion sickness during vehicle travel as measured by the MSSS.

Secondary Objectives:

- 1. To assess the effects of tradipitant 170 mg on the symptoms of motion sickness as measured by subjective parameter MSAQ.
- 2. To assess the effects of tradipitant 170 mg on the symptoms of motion sickness as measured by subjective parameter LTMSQ.

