- 3. To assess the effects of tradipitant 170 mg on the symptoms of motion sickness as measured by subjective parameter SDQ.
- 4. To assess the effects of tradipitant 170 mg on the symptoms of motion sickness as measured by subjective parameter PGI-S.
- 5. To assess the effects of tradipitant 170 mg on the symptoms of anxiety as measured by STAI-6.
- 6. To assess the safety and tolerability of a single oral dose of tradipitant 170 mg.

Overall Design: This is a randomized, double-blind placebo-controlled trial to investigate the efficacy and safety of a single 170 mg oral dose of tradipitant in motion sickness affected male and female subjects during vehicle travel.

The screening phase will consist of the subject taking the motion sickness eligibility questionnaire (MSEQ) to assess their susceptibility to motion sickness. Following this questionnaire, the subject will be interviewed to understand their history of motion sickness. If the subject meets pre-defined criteria as being eligible based on the motion sickness eligibility questionnaire and interview, they will proceed to the next step of a screening visit at a clinical site with a physician and simultaneously a lab visit for a blood draw. If the subject passes the medical visit screen and blood draw based on inclusion and exclusion criteria they will proceed to the evaluation phase.

Eligible subjects will be randomized 1:1 to tradipitant 170 mg or placebo. Eligible subjects will be instructed to take tradipitant 170 mg or placebo approximately 60 minutes prior to entering the vehicle. Vehicle travel assessment will occur either in a motor vehicle (2A) or boat (2B). Subjects will be driven on a pre-determined route for approximately 120-240 minutes during motor vehicle travel or approximately 90-300 minutes during boat travel. The MSSS questionnaire will be completed approximately every 30 minutes of vehicle travel and the STAI-6 will be completed at the beginning of vehicle travel, prior to drug administration.

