After the completion of the vehicle travel, subjects will complete several questionnaires including a motion sickness severity scale questionnaire (MSSS), a travel questionnaire for the subject to assess the likelihood of their travel experience to induce motion sickness based on experience scored from 1-9 (LTMSQ), a motion sickness assessment questionnaire (MSAQ), a questionnaire to record the duration of symptoms (SDQ), the 6-item Spielberger State-Trait Anxiety Inventory (STAI-6), and the Patient Global Impression of Severity Questionnaire (PGI-S). All questionnaires will be submitted for analysis. Subjects will then return for an EOS visit within 7 days of visit 2.

Statistical Methods: Motion sickness symptoms will be assessed by the MSSS questionnaire, with the other questionnaires serving as secondary endpoints. Motion sickness symptoms as measured by MSSS will be assessed by analysis of variance with the treatment group, vehicle, and site, if more than one site, as main effects. The primary efficacy analysis will be based on the ITT population. The statistical analyses will be detailed in the statistical analysis plan.

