1. STATISTICS

1.1. Sample Size and Accrual

A sample size of up to 75 subjects per arm (150 total) will provide around 86% power to detect a 0.8 point difference in motion sickness severity between Tradipitant and Placebo, with the standard deviation of motion sickness severity assumed to be around 1.6.

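### Does the primary ANOVA treat repeated MSSS readings as independent, and is the 86% power tied to no defined variable?

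*Combined protocol and SAP*

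**What the plan says.** The Synopsis limits the primary objective to effects "on the symptoms of motion sickness during vehicle travel as measured by the MSSS". Under Overall Design it states that "The MSSS questionnaire will be completed approximately every 30 minutes of vehicle travel", and it lists the MSSS again among the questionnaires filled in once the trip is over. Trips last "approximately 120-240 minutes during motor vehicle travel or approximately 90-300 minutes during boat travel".

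Section 1.3.1 defines the endpoint in one sentence: "The primary endpoint is motion sickness severity assessed by the MSSS questionnaire". It then says: "The primary analysis method is ANOVA with the treatment group, vehicle, and site, if more than one site, as main effects". No time point or summary (worst, mean, last) is named, and the model has no subject, time or covariance term.

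Section 1.1 states that "A sample size of up to 75 subjects per arm (150 total) will provide around 86% power" for a difference of 0.8 points, "with the standard deviation of motion sickness severity assumed to be around 1.6". It does not say which MSSS value has that difference and SD.

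Sections 1.2.1 and 1.3.1 leave the detail to a statistical analysis plan. Section 1.2.1 requires it to describe the methodology completely and to be final before unblinding. Section 1.3.2 applies the primary analysis to the other questionnaires as well.

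**The concern.** The schedule yields several MSSS readings per subject, while the model has room for one. If an analyst passed every reading to the stated ANOVA, each subject would count several times, the standard error would be too small, and the only primary test would reject far too often under no effect.

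If one value per subject is meant, the text does not say which. Worst, mean, last on-board and post-travel scores are different variables, with different SDs and possibly different treatment effects. The post-travel score also fits poorly with an objective about symptoms during travel. A power figure quoted for an unnamed variable might then not describe the test that is run.

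**Working it through.** **1. Inputs.** From Section 1.1: 75 per arm, difference 0.8, SD 1.6. From Section 1.2.1: two-sided alpha 0.05. From the Synopsis: one reading per 30 minutes, and the trip lengths. The within-subject correlation (rho) and the time course of the effect are not in the documents, so every figure that uses them is an assumption.

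**2. Readings per subject.**
- Motor vehicle: 120/30 = 4 to 240/30 = 8.
- Boat: 90/30 = 3 to 300/30 = 10.
- One more after travel gives 4 to 11 in total. The post-travel reading may coincide with the last on-board one.

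**3. The plan's power, one value per subject.**
- Noncentrality: 0.8 / (1.6 × √(2/75)) = 3.06.
- Normal approximation: Φ(3.06 − 1.96) = 86.5%.
- Noncentral t with 148 degrees of freedom: 86.0%.

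The stated 86% reproduces with 150 independent values, one for each subject. Only the ratio 0.8/1.6 = 0.5 matters, so the result holds for any per-subject variable with that ratio.

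**4. What pooling would do.** With m equally correlated readings per subject, the design effect is DE = 1 + (m − 1)rho, and the actual two-sided error is 2 × (1 − Φ(1.96/√DE)). For example, m = 4 and rho = 0.5 gives DE = 2.5 and an error of 0.215.

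| m | rho 0.3 | rho 0.5 | rho 0.7 | rho 0.9 |
|---|---|---|---|---|
| 4 | 0.155 | 0.215 | 0.266 | 0.308 |
| 11 | 0.327 | 0.424 | 0.488 | 0.535 |

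Simulation at rho 0.5 gives 0.215 for m = 4 and 0.419 for m = 11. The inflation would be severe, but it belongs to an analysis that the plan does not describe.

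**5. Which reading of the plan fits.** Three features point to one value per subject:
- the model has no subject or time term, which is correct only for such data;
- the sample size uses one difference, one SD and a count of subjects;
- Section 1.3.2 uses the same model for MSAQ, SDQ, LTMSQ and PGI-S, which the Synopsis describes only as completed after travel. STAI-6 is the exception, being taken before dosing as well.

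**6. Does the choice of value matter?** A simulation used 75 per arm, 3 to 10 on-board readings and rho 0.3, 0.5 and 0.7, and assumed that 1.6 is the SD of a single reading.

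| Value analysed | Error rate, no effect | Power, 0.8 at every reading | Power, effect rising 0.2 per reading to 0.8 |
|---|---|---|---|
| Mean | about 5% | 94–99.7% | 72–93% |
| Worst | about 5% | 91–98% | 60–77% |
| Last on board | about 5% | 86–87% | 83–84% |

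Every choice gives a valid test. The power columns do not show that 86% fits only a single reading, because that was built in by assigning 1.6 to a single reading. If 0.8 and 1.6 describe the mean or the worst score, 86% is correct for that score.

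**The case for a change.** The strongest case for a change is that the choice of MSSS value is the endpoint itself, not a detail of method, and that Section 1.1 already quotes a power for it. Two statisticians working from Section 1.3.1 could analyse different variables. In the same simulation with no true effect, the chance that at least one of mean, worst and last is significant is about 10%, 10% and 8% at correlations of 0.3, 0.5 and 0.7. The post-travel reading is not excluded by name. Boat trips vary more than threefold in length, so worst, mean and last do not mean quite the same thing for every subject.

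Part of this stands. The available text does not name the value and does not tie 0.8 and 1.6 to it, and power could differ from 86% if they were meant for another summary. But the 8–10% arises only if the value is picked after seeing results, which a plan finalised before unblinding rules out. The primary objective already points to readings taken during travel. Varying trip length argues against any one summary being plainly best: a worst score has more chances to be high on a long trip, a mean dilutes a late effect, and a last score depends on when the trip ends.

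The text also cites an appendix and a section that it does not contain (Appendix 20.1 and Section 11.1.3), so it appears to be an extract. Whether the value is defined elsewhere cannot be checked.

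**Conclusion.** The concern does not call for a change. The claim that the plan treats repeated readings as independent fails: no section says so, the stated ANOVA suits one value per subject, and 86.0% reproduces on that basis. Error rates of 0.16 to 0.54 would follow only from pooling all readings, at correlations that are assumed. The claim that 86% belongs to one particular reading fails too, since it rests on treating 1.6 as a single-reading SD.

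What is left is an unwritten definition of the per-subject MSSS value. The plan assigns that kind of detail to a SAP completed before unblinding, and analysts would be expected to fill it sensibly there, together with the variable to which 0.8 and 1.6 refer. Any of the usual values keeps the error rate near 5%, and preferring one is a trade-off. This conclusion assumes that one value per subject is analysed and that it is fixed before unblinding, as Section 1.2.1 requires of the SAP.

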1.2. Statistical Methods and Analysis Plan

1.2.1. General

This section describes the planned statistical analyses in general terms. A complete description of the methodology will be specified in a statistical analysis plan (SAP), which will be finalized prior to unblinding. Any changes in the statistical methods described in this protocol that occur prior to unblinding will be documented in the statistical analysis plan and will not require a protocol amendment.

Statistical hypothesis testing will be performed at two sided alpha level of 0.05. For continuous variables, population size (N for sample size and n for available data), the mean, the standard deviation (SD), the median, the minimum and maximum values will be tabulated. For categorical variables, population size and frequencies in each category will be tabulated.

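### The primary ANOVA leaves out the pre-randomisation MSEQ; if a graded score is on record, pre-specifying it as one covariate is a cheap and possible, not assured, gain in power

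*Combined protocol and SAP*

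**What the plan says.** The primary model is given twice. The Synopsis (Statistical Methods) says: "Motion sickness symptoms as measured by MSSS will be assessed by analysis of variance with the treatment group, vehicle, and site", with site to be included only if there is more than one. Section 1.3.1 repeats this: "The primary analysis method is ANOVA with the treatment group, vehicle, and site, if more than one site, as main effects". The Synopsis plans one centre, so the working model is treatment plus vehicle.

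The Synopsis (Overall Design) begins screening with "the motion sickness eligibility questionnaire (MSEQ) to assess their susceptibility to motion sickness". An interview follows, and the subject moves on to the medical screen "If the subject meets pre-defined criteria as being eligible based on the motion sickness eligibility questionnaire and interview". Randomisation comes after that. No scoring, range or cut-off for the MSEQ is given.

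Section 1.1 bases the sample size on up to 75 subjects per arm, a difference of 0.8 points and power of around 86%, "with the standard deviation of motion sickness severity assumed to be around 1.6". It does not say whether that SD is before or after adjustment for any baseline variable.

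Section 1.2.1 qualifies the whole: "This section describes the planned statistical analyses in general terms". Full detail is left to an SAP finalised before unblinding, and changes of method that occur "prior to unblinding will be documented in the statistical analysis plan and will not require a protocol amendment".

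**The concern.** A measure of susceptibility taken before randomisation cannot be affected by treatment. By its stated purpose it should bear on how sick a subject becomes during travel. If it predicts MSSS, leaving it out of the model leaves explainable variation in the residual, so the treatment effect is estimated less precisely than the data allow, and a chance imbalance in susceptibility between arms goes uncorrected. The choice has to be made before unblinding, because a covariate chosen afterwards would not be credible.

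What is at stake is a modest amount of power, not the validity of the trial.

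**Working it through.** **Inputs from the protocol.** 75 per arm, difference 0.8, SD 1.6, power around 86% (section 1.1); two-sided alpha 0.05 (section 1.2.1); 1:1 allocation and one centre (Synopsis).

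**Assumptions.** The SD of 1.6 is the unadjusted SD. The MSEQ enters as one continuous covariate. Its within-arm correlation with MSSS among randomised subjects is r. The documents do not give r, so 0 to 0.3 is shown.

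**Step 1: reproduce the plan's figure.**
- Standard error: 1.6 × √(2/75) = 0.2613.
- Noncentrality: 0.8 / 0.2613 = 3.062.
- Two-sided noncentral-t power: 86.04% on 148 df and 86.03% on 147 df (treatment plus vehicle). The normal approximation gives 86.5%.

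The stated figure holds without any covariate.

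**Step 2: add the MSEQ.** The residual SD becomes 1.6 × √(1 − r²). The variance of the treatment effect is multiplied by 1 + 1/146, the average cost of chance imbalance in the covariate, and the test has 146 df. The standard error relative to the unadjusted one is √[(1 − r²)(1 + 1/146)].

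| Assumed r | Relative SE | Power | Change from 86.0% |
|---|---|---|---|
| 0 | 1.003 | 85.8% | -0.2 |
| 0.1 | 0.998 | 86.1% | +0.1 |
| 0.2 | 0.983 | 87.2% | +1.1 |
| 0.3 | 0.957 | 88.8% | +2.8 |

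Simulation of treatment plus vehicle with and without the covariate (100,000 trials per r) gave changes of -0.2, +0.1, +1.2 and +2.9 points. In a separate simulation the type I error of the ANCOVA was 4.8 to 5.2%.

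**Step 3: break-even.** Setting (1 − r²)(1 + 1/146) = 1 gives r² = 1/147 = 0.0068, so r is about 0.08. This is an average over trials. In simulation the adjusted confidence interval was wider than the unadjusted one in 61% of trials at r = 0.084, 53% at r = 0.1 and 19% at r = 0.186. Near break-even, then, a single trial's interval is about as likely to widen slightly as to narrow. Clear narrowing needs r of about 0.2 to 0.3 or more; the average is then about 1.7% to 4.3% (1 − 0.983 and 1 − 0.957).

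**Step 4: effect of selection.** Subjects enter partly on the MSEQ, which narrows its range. As an illustration only, suppose entry keeps the upper half of a normal score, so that its SD falls to 0.603 of the unselected value. Then r = 0.3 before selection becomes 0.3 × 0.603 / √(1 − 0.09 + 0.09 × 0.603²) = 0.186, and power is 87.0%, a gain of about 0.9 points rather than 2.8.

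**The case against.** The strongest reply is that no defect has been shown. ANOVA without a prognostic covariate is a legitimate primary analysis in a randomised trial, the power calculation is sound, and the preference for ANCOVA rests on facts the documents do not give. The MSEQ is described only as an eligibility questionnaire judged together with an interview. If only pass or fail is kept, every randomised subject has the same value and there is nothing to adjust for. The protocol also defers detail to an SAP, which might already include a covariate.

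Most of this stands. It makes the point conditional and limits it to an optional improvement. The deferral does not dispose of it, however: the model terms are stated in two places and hold unless the SAP changes them.

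Three stronger readings are tempting, and the documents do not support them:

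- **That the trial is underpowered or its primary analysis unsound.** The stated power reproduces, and randomisation makes the ANOVA valid.
- **That adjustment would bring a large gain.** At r = 0.5 the same formula gives 93.8%, or +7.8 points, but nothing in the documents supports that correlation, and selection on the MSEQ works against it.
- **That any r above 0.08 narrows the interval.** That threshold concerns average power only, as the simulated intervals show.

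The SD is a further limit. If 1.6 already reflects adjustment for susceptibility, the gain cannot be added to the stated 86%.

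**Conclusion.** The point stands as a cheap, conditional improvement and not as an error. Adding the MSEQ to the MSSS model as one continuous covariate would change power by about -0.2 to +2.8 points for r between 0 and 0.3, and selection on the MSEQ probably moves the result towards the lower end. The possible loss is smaller than the possible gain, which is the case for acting; the range crosses zero, so the gain is not assured.

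The conclusion rests on a graded MSEQ value being recorded and varying among randomised subjects, on the assumed range of r, and on 1.6 being the unadjusted SD. None of these can be confirmed from the documents.

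**What to change.** Before unblinding, find out whether the MSEQ record holds a graded result that varies among randomised subjects.

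- **If it does:** pre-specify in the SAP an ANCOVA of MSSS with treatment, vehicle, site if more than one, and the MSEQ score as a single continuous covariate. Keep the ANOVA without the MSEQ as a sensitivity analysis.
- **If only pass or fail is recorded:** make no change.

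The recommendation concerns the MSSS analysis only. Section 1.3.2 has the secondary questionnaires follow the primary method, so the SAP should say which model applies to them; the documents give no basis for settling that here.

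The cost is one check of the record, a short SAP paragraph, one degree of freedom, and about 0.2 power points if the MSEQ turns out to be uninformative. Under section 1.2.1 no protocol amendment is needed. No new data are needed, provided the graded result has been kept.

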1.3.2. Secondary Efficacy Analysis

The secondary endpoints from other questionnaires (MSAQ, SDQ, LTMSQ, STAI-6, PGI-S) will be analyzed in the same way as the primary endpoint. Other statistical methods may also be used as deemed appropriate. The details will be provided in the SAP.

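### Does the primary ANOVA need scheduled trip length as a covariate, given the wide range of trip durations?

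*Combined protocol and SAP*

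**What the plan says.** Section 1.3.1 names the model: "The primary analysis method is ANOVA with the treatment group, vehicle, and site, if more than one site, as main effects". The synopsis (Statistical Methods) agrees: "analysis of variance with the treatment group, vehicle, and site, if more than one site, as main effects". The synopsis lists one study centre, so in practice the terms are treatment and vehicle. No trip-length term is named.

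Duration appears only as an approximate range per vehicle type: "If motor vehicle travel, one drive lasting approximately 120-240 minutes" and "If boat travel, one trip lasting approximately 90-300 minutes on the moving vessel". Overall Design repeats both ranges and refers to a route in the singular: "Subjects will be driven on a pre-determined route for approximately 120-240 minutes during motor vehicle travel or approximately 90-300 minutes during boat travel". On measurement it says: "The MSSS questionnaire will be completed approximately every 30 minutes of vehicle travel". The text does not say whether planned length differs between trips of the same type, or which summary of the repeated MSSS readings is the endpoint.

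Section 1.1 gives 75 per arm, a difference of 0.8, an SD of about 1.6 and around 86% power. Section 1.2.1 leaves the full method to an SAP finalized before unblinding; changes from the protocol's methods made before then "will be documented in the statistical analysis plan and will not require a protocol amendment". Under section 1.3.2 the secondary questionnaires "will be analyzed in the same way as the primary endpoint".

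**The concern.** The longest boat trip allowed is more than three times the shortest (300/90 = 3.3), and the longest drive is twice the shortest (240/120 = 2). Motion sickness may build with exposure, and a longer trip gives more readings and so more chances of a high one. The vehicle term removes only the average boat-car difference. Any effect of length within a vehicle type stays in the error term. Planned length is set before travel, so treatment cannot affect it, and adjusting for it would be legitimate. If length varied and mattered, the trial would be giving up power that one extra SAP sentence could recover.

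**Working it through.** **1. The plan's own figure.** From section 1.1: n = 75 per arm, difference 0.8, SD 1.6; from section 1.2.1: two-sided alpha 0.05. The noncentrality is 0.8 / (1.6 × √(2/75)) = 3.06. With 148 degrees of freedom the power is 86.0%; the normal approximation gives 86.5%. The stated figure reproduces.

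**2. Validity.** Allocation is 1:1 at random, so trip length is balanced between arms in expectation. Leaving it out biases nothing. In simulated worst-score trials (five cases, 20,000 runs each) type I error was 4.6-5.1%, with or without the covariate. Only precision is in question.

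**3. Cost of a useless covariate.** Chance imbalance inflates the variance of the treatment contrast by about 1 + 1/146. Power goes from 86.0% to 85.8%, a loss of about 0.2 points.

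**4. Size of the gain.** The documents give no relation between MSSS and time, so the following are assumptions: single-reading SD 1.6; correlation 0.6 between a subject's readings; a rise of 0, 0.1 or 0.2 points per 30-minute reading; lengths spread evenly over the full stated ranges unless noted. The ranges allow 90/30 = 3 to 300/30 = 10 readings by boat and 120/30 = 4 to 240/30 = 8 by car.

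*Last score, closed form.* The SD of the number of readings is √(63/12) = 2.29 by boat and √(24/12) = 1.41 by car. With a rise of 0.2 per reading, the SD without the covariate is:
- boat: √(1.6² + 0.458²) = 1.66, power 83.3%;
- car: √(1.6² + 0.283²) = 1.62, power 85.0%.

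With the covariate and its cost, power is 85.8%. The net gains are 85.8 − 83.3 = 2.5 and 85.8 − 85.0 = 0.8 points. With no rise over time the net result is −0.2.

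*Worst score, 400,000 simulated subjects per case.* The cost is about 0.16 points at this power level and is included in the last two columns.

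| Rise of 0.2 per reading | Residual SD without → with | Power without | Power with | Net |
|---|---|---|---|---|
| All boat | 1.510 → 1.416 | 89.7% | 92.9% | +3.2 |
| Half and half | 1.483 → 1.417 | 90.7% | 92.8% | +2.1 |
| All car | 1.453 → 1.415 | 91.8% | 92.9% | +1.1 |

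Other cases:
- Worst score, all boat, rise of 0.1: about +1.3 net. No rise: about +0.4.
- Worst score, rise of 0.2 that levels off at reading 4: about +0.9 net by boat and +0.2 to 0.3 by car. The last and mean scores then gain nothing.
- Lengths only in the middle of the ranges (boat 150-240, car 150-210 minutes): at most 0.7 before cost and about 0.6 after, even with the 0.2 rise.
- Mean score: 0.1-0.6 before cost with the 0.2 rise (correlations 0.4-0.8), and a small loss with no rise (95.8% to 95.7% by direct regression).
- Length constant within vehicle type: no gain, because the vehicle term already carries it.

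**5. What the larger gains require.** A rise of 0.2 per reading from reading 3 to reading 10 is 7 × 0.2 = 1.4 points, well above the 0.8-point treatment effect the trial is sized for. It must continue without levelling off for up to five hours, and planned lengths must fill the whole range.

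**6. What the text supports.** The route is singular and fixed in advance, and the durations are approximate. The ranges read equally well as tolerances for how long a trip turns out to last. On that reading planned length is constant within a vehicle type and the covariate is redundant. Variation from traffic or sea state would stay in the error term, because a subject's actual time on board comes after randomization, could be affected by treatment, and should not be used.

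**The case for a change.** The strongest argument is asymmetry: at most about 0.2 points lost against about 3 gained with lengths spread evenly. If half of the trips sat at each extreme of the ranges, the gain for a worst score could reach 9.3 points before cost (all boat, rise of 0.2, correlation 0.4). If the SD of 1.6 describes the analysed score and not a single reading, the all-boat worst-score case moves from about 86.0% to about 90.0%, slightly more than in the table. A separate simulation, with slopes of 0.25, 0.5 and 0.75 points per hour, gave 85.6% to 85.9%, 86.4% to 88.1% and 87.0% to 90.7%. The sponsor knows its routes, the SAP route is open, and adding the term after unblinding would be post hoc.

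The arithmetic stands, and so does the point that a prespecified planned-length covariate is valid and cheap. What does not follow is that leaving it out is a fault. The same asymmetry can be claimed for many baseline variables with a plausible link to the outcome. A single linear term removes only a linear effect common to boat and car, so even in the favourable case some noise would remain. And since the model detail is left to an SAP that is not part of the supplied text, absence of the term from the final analysis is not established either.

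**Conclusion.** The concern does not hold. The planned ANOVA is valid, it already adjusts for the one travel condition the design splits on, and its power statement is correct. With evenly spread lengths and correlation 0.6, the net effect of adding planned trip length runs from about −0.2 to about +3.2 power points. The top of that span needs a worst score, all-boat travel, lengths over the full range and a steady rise of 0.2 per reading. Mid-range lengths leave at most about 0.6, and constant length leaves nothing. Only the extreme half-and-half split of lengths goes clearly beyond this, and nothing in the documents points to it. The conclusion rests on the assumed time trends and correlations, since the protocol gives none. Record of planned trip lengths that differ widely within a vehicle type, together with a worst or last score as endpoint, would make the covariate more attractive, but still as an option for precision. The unstated MSSS summary is a separate matter that this point does not settle.
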